11.2 Adverse Event Documentation

Due to the complex medical condition of the post-transplant patient, monitoring for adverse events will focus on the following events beginning with the 1st dose of Pregnyl® and continuing for 4 weeks after the last dose. Any of these events will be documented on the study specific case report form:

- death
- anaphylaxis
- thromboembolic event
- Grade 3-4 skin injection site reaction
- Grade 3 headache
- Grade 3 gynecomastia
- Grade 3-4 ascites

In addition, the following events occurring by day 21 after the 1st dose of Pregnyl® are considered a dose limiting toxicity (DLT) and should be reported as such for patients enrolled in the Phase I component per [section 11.4](#):

- In males and females: Grade 2-4 thromboembolic event (CTCAE v4)
- In males and females: Grade 3-4 ascites (CTCAE v4)
- Specific to females: Grade 3-4 ovarian hyperstimulation syndrome, defined as the rapid development of enlarged, cystic, painful ovaries, Note: as there is no CTCAE grading for this event, the generic grading will apply as follows:

Grade	Description
1	mild; asymptomatic or mild symptoms; clinical or diagnostic observations
2	moderate; minimal or non-invasive intervention indicated

Grade	Description
3	severe or medically significant but not immediately life-threatening; hospitalization or prolongation of hospitalization indicated
4	life-threatening consequences; urgent intervention indicated

For the Phase II expansion cohort, an early study stopping rule was developed for excessive Grade 4/5 non-hematologic, non-infectious treatment probably or definitely attributed to the study drug occurring by day 28 after the last dose of Pregnyl® and is reportable per [section 11.4](#). Refer to [section 13.4](#) for details.

For both cohorts, relapse of the patient's malignancy and/or development of a new one occurring 4 weeks after the last dose is reportable per [section 11.4](#).

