HCG is a hormone critical for the development of maternal immune tolerance towards a fetus during pregnancy, arguably the most commonly encountered and effective example of induced immune tolerance in nature. HCG induces immune tolerance in pregnancy by mechanisms including induction of indoleamine 2,3 dioxygenase (IDO) and expansion of endogenous regulatory T cells (Tregs), both of which are protective against GVHD. Therefore, hCG may be effective in promoting immune tolerance in aGVHD. Importantly, a urinary-derived preparation of hCG has already shown early promise in inducing tolerance and reversing organ damage without untoward toxicity in 12 of 20 (60%) of patients with heavily pre-treated patients with steroid-refractory or intolerant chronic GVHD [22].

The objective of this study is to test for the first time the use of supplemental EGF and hCG (Pregnyl®) as an adjunct to facilitate improved mucosal healing and immune tolerance in addition to accepted, standard immunosuppressive therapy in the setting of high-risk (Arm 1) and steroid-refractory (Arm 2) aGVHD. Our central hypothesis is that administration of urinary hCG and EGF will provide (a) EGF for facilitation of gastrointestinal healing and (b) hCG for induction of immune tolerance, while not worsening the rates of infectious or other complications, in patients with severe aGVHD. However, the optimal supplemental doses of EGF necessary to achieve an epithelial restitution effect are not known. Therefore, this study will use the Continuous Reassessment Method (CRM) to test up to five dose levels of Pregnyl® in order to identify the maximum tolerated dose (MTD) by each patient cohort (high-risk (arm 1), steroid dependent (arm 2A) and steroid-refractory (arm 2B)). We will determine pharmacokinetics of both the EGF and hCG components of urinary HCG and identify correlative biomarkers of aGVHD response. The pharmacokinetic and correlative studies would not be possible without intercollegiate collaborations. The knowledge gained from these aims will provide critical feasibility, preliminary safety, and correlative data for efficacious dose selection and identification of leading biomarkers for the phase II expansion of this trial. These data will be necessary to successfully compete for National Institutes of Health or similar funding for a larger scale, multicenter trial, if the approach proves to be feasible, tolerable, and efficacious in this initial study.

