7.5 Duration of Study Therapy

Arm 1 (high-risk aGVHD): Study treatment will be for a minimum of 7 days with study therapy continuing for an additional 5 weeks if a complete or partial response is documented at the initial response evaluation. Non-responders at 7 days will be taken off study therapy and treated at the discretion of the treating physician. The treating physician may remove patients from study participation sooner if concerns regarding safety emerge prior to completing 7 days on protocol.

Arm 2A and 2B (steroid-refractory/dependent aGVHD): Study treatment will be for a minimum of 14 days with study therapy continuing for an additional 5 weeks if a complete or partial response is documented at the initial response evaluation. Non-responders at 14 days will be taken off study

therapy and treated at the discretion of the treating physician. The treating physician may remove patients from study participation sooner if concerns regarding safety emerge prior to completing 14 days on protocol.

An exception to the above is if a patient experiences an event that fits the definition of a dose limiting toxicity (Grade 2-4 thromboembolic event, Grade 3-4 ascites or Grade 3-4 ovarian hyperstimulation syndrome). Study treatment will be permanently discontinued in this situation.

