NOTE: For Arm 2B, Dose level 5, in order to avoid using vials from more than one Lot of study product, the maximum dose is either (1) the contents of a single 10,000 IU vial, or (2) a maximum dose of 10,000 IU from multiple vials. All vials used should be from the same Lot.

IMPORTANT: RECONSTITUTED SOLUTION IS STABLE FOR 60 DAYS WHEN REFRIGERATED.

PRECAUTIONS

1. General: Since androgens may cause fluid retention, hCG should be used with caution in patients with cardiac or renal disease, epilepsy, migraine, or asthma.
2. Pediatric Use: Induction of androgen secretion by hCG may induce precocious puberty in pediatric patients treated for cryptorchidism. Therapy should be discontinued if signs of precocious puberty occur.
3. Geriatric Use: Clinical studies of PREGNYL® (chorionic gonadotropin for injection, USP) and its generic equivalent did not include subjects aged 65 and over.
4. ADVERSE REACTIONS: Headache, irritability, restlessness, depression, fatigue, edema, precocious puberty, gynecomastia, pain at

the site of injection. Hypersensitivity reactions, both localized and systemic in nature, have been reported.

9 Disease Reassessment and Response Definitions

Participants will be staged according to the Minnesota grading schema below:

GUIDE FOR GVHD STAGING

ORGAN	CLINICAL STAGE	
SKIN	1 = Rash <25% BSA	
	2 = Rash 25-50% BSA	
	3 = Generalized erythroderma	
	4 = Generalized erythroderma with bullous formation or desquamation	
LOWER GI	ADULT	PEDS
	0 = <500	(<280ml/m ²)
	1 = 500-1000	(281-555ml/m ²)
	2 = 1000-1500	(556-833ml/m ²)
	3 = >1500	(>834ml/m ²)
	4 = Severe abdomen pain with or without ileus, or stool with frank blood	
Liver	1 = Bili 2.1-3.0	
	2 = Bili 3.1-6.0	
	3 = Bili 6.1-15.0	
	4 = Bili >15.1	
UPPER GI	0 = No prolonged nausea or vomiting	
	1 = Persistent nausea, vomiting or anorexia	

Overall Grade	Organ Stage			
	Skin	Liver	Lower GI	Upper GI
I	1-2	0	0	0
II	3	1	1	1
III	-	2-4	2-3	
IV	4	-	4	

Response will be based on the following definitions:

- **Complete Response (CR):** a Stage of 0 for all organs with no additional intervening therapy for their GVHD.
- **Partial Response (PR):** improvement by at least 1 stage in all involved organs without progression in others with no additional intervening therapy for their GVHD.
- **Mixed Response (MR):** improvement in one organ with deterioration in another organ manifesting symptoms of GVHD or development of symptoms of GVHD in a new organ.

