13.4 Early Stopping Rule

During Phase I CRM, the trial will stop if the posterior probability that the lowest dose is more toxic than the target is greater than 90%. Stopping rules will also be employed to monitor excess toxicity outside of the phase I trial. Stopping rule was developed using Pocock stopping boundaries [32]. The stopping rule will be monitored for Arm 1, 2A and Arm 2B separately.

Early Stopping Rule for Toxicity

Stopping rules were developed for excessive Grade 4/5 non-hematologic, non-infectious toxicity attributed to the study drug occurring by day 28 after the last dose of hCG. The goal is to construct a boundary based on toxicity such that the probability of early stopping is at most 10% if the toxicity rate is equal to 20% and assuming 13 more patients of each arm are enrolled after phase I. Given these parameters, the upper stopping boundary for toxicity is 2 events out of 2 patients, 3 events out of 3 patients, 5 out of 8, or 6 at any time. If the true toxicity rate is as high as 50% then chance of early stopping is 80% and the expected sample size is 7.3.

14 Conduct of the Study

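### The targeted adverse-event list in 11.2 does not name ovarian hyperstimulation outside phase I or after day 21, or precocious puberty at any time, so non-serious cases are not systematically recorded

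*Combined protocol and SAP*

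**What the plan says.** **The list (11.2).** Citing the medical complexity of post-transplant patients, the protocol says that "monitoring for adverse events will focus on the following events beginning with the 1st dose of Pregnyl", with collection running until four weeks past the final dose. The seven items are death, anaphylaxis, thromboembolic event, Grade 3-4 injection-site reaction, Grade 3 headache, Grade 3 gynecomastia and Grade 3-4 ascites. It adds: "Any of these events will be documented on the study specific case report form".

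**The DLTs (11.2).** A separate paragraph names Grade 2-4 thromboembolism, Grade 3-4 ascites and Grade 3-4 ovarian hyperstimulation by day 21. These "should be reported as such for patients enrolled in the Phase I component". A generic four-grade scale is supplied for hyperstimulation because CTCAE has none.

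**Discontinuation (7.5).** The same three event types, with hyperstimulation at Grade 3-4, are an exception to the planned treatment duration: "Study treatment will be permanently discontinued in this situation". The sentence does not mention phase.

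**Drug information (8.1).** A paediatric precaution mentions precocious puberty in boys treated for cryptorchidism and continues: "Therapy should be discontinued if signs of precocious puberty occur". The adverse-reaction list that follows names precocious puberty without that qualifier. Section 5.1 admits patients from age 0 to 76 in every arm.

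**Where the list is used.** Both activity schedules in section 10 define toxicity assessment by reference to 11.2. Section 12.1 says that targeted adverse events go into the study database. Safety is a secondary objective (1.2), and the phase II extension is meant to confirm it (13.1).

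**The concern.** The three DLT types are treated unequally. Two are collected by name in every patient over the whole exposure period. The third is collected by name only in phase I and only for three weeks, while responders keep receiving the drug for about five more weeks. Precocious puberty is the paediatric effect that the drug section warns of, and it has no place on the list.

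What is at stake is what the safety summary can say. Section 13.3 can tabulate only what was recorded. If hyperstimulation or pubertal signs do not appear in the final tables, a reader could not tell whether non-serious cases were absent or were not asked about. Section 10.1 adds a further use for these data: it hypothesises that any hCG-induced rise in sex hormones will be reversible and unaccompanied by adverse events. Hormones are measured to day 56, but of the two reactions in 8.1 that are plainly hormonal (gynecomastia and precocious puberty), the list carries only gynecomastia, at Grade 3.

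**Working it through.** The plan gives no figure on this point to reproduce. The check sets the sections side by side and then counts doses and patients.

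**1. Routes by which each event would be recorded**

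| Event | 11.2 list, both phases, to four weeks past final dose | 11.2 DLT, phase I, by day 21 | SAE form (11.3) | Stopping rule after phase I (13.4) |
|---|---|---|---|---|
| Thromboembolism | yes | Grade 2-4 | if serious | Grade 4/5, attributed |
| Ascites | Grade 3-4 | Grade 3-4 | if serious | Grade 4/5, attributed |
| Ovarian hyperstimulation | **no** | Grade 3-4 | if serious | Grade 4/5, attributed |
| Precocious puberty | **no** | no | if serious | Grade 4/5, attributed |

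On the generic scale in 11.2, Grade 3 hyperstimulation means that hospitalization is indicated, and Grade 4 means a threat to life. Either would normally meet the SAE definition in 11.1. What has no named route, in phase II or after day 21, is Grade 1-2 hyperstimulation. Pubertal signs would usually not be serious by the 11.1 definition, so for them the gap covers most cases, in both phases.

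**2. Share of a responder's doses after day 21**

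Inputs: lead-in doses every other day, 4 in Arm 1 (7.1) and 7 in Arms 2A and 2B (7.2, 7.3); then 10 maintenance doses twice weekly, starting on day 9-12 (Arm 1) or day 15-17 (Arms 2A and 2B). Assumption: twice weekly means alternating gaps of 3 and 4 days.

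- Arm 1, start day 9: days 9, 12, 16, 19, 23, 26, 30, 33, 37, 40. Six fall after day 21: 6/14 = 43%.
- Arm 1, start day 12: days 12, 15, 19, 22, 26, 29, 33, 36, 40, 43. Seven fall after day 21: 7/14 = 50%.
- Arms 2A and 2B, start day 15: days 15, 18, 22, 25, 29, 32, 36, 39, 43, 46. Eight fall after day 21: 8/17 = 47%.
- Arms 2A and 2B, start day 17: days 17, 20, 24, 27, 31, 34, 38, 41, 45, 48. Again 8/17 = 47%.

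Starting with the 4-day gap leaves these counts unchanged.

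**3. Patients enrolled after phase I (13.2)**

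Total per arm minus the 20 phase I patients:

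- Arms 1 and 2A, each: 33 − 20 = 13 to 44 − 20 = 24.
- Arm 2B: 37 − 20 = 17 to 44 − 20 = 24.

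For none of these patients does 11.2 name hyperstimulation. The documents do not say how many will be female or pre-pubertal, so the number at risk is unknown.

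**4. Wording of the hyperstimulation DLT**

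The synopsis and 13.1 give it no grade limit. Sections 7.1-7.3 and 11.2 limit it to Grade 3-4. Under the synopsis and 13.1, a Grade 1-2 case in phase I is a DLT; under 11.2 it is not reported as one. This would feed directly into the dose-finding model.

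**The case against.** The strongest reply is that the list is a stated focus, chosen because background morbidity is high, and does not claim to be exhaustive. Other routes run beside it: the SAE form for any serious event in both phases (11.3), the phase II rule for "excessive Grade 4/5 non-hematologic, non-infectious toxicity attributed to the study drug" (13.4), and the IND annual report (11.4). Severe hyperstimulation would normally reach the SAE form. Section 2 puts severe reactions of this kind below 1%, so even 24 women in one arm would give fewer than 24 × 0.01 = 0.24 expected events. Four of the seven listed items also carry a Grade 3 or 3-4 threshold, so a focus on severe events looks deliberate.

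Much of this stands, and it rules out several stronger readings that a reader might infer:

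- *That the list is closed and hyperstimulation goes unrecorded in phase II.* Not supported: serious cases have a route, and a count of them could be reported.
- *That 7.5 and 8.1 contradict each other on precocious puberty.* They do not. Section 7.5 lists the DLT exceptions and lets the physician withdraw a patient over safety concerns; 8.1 is a drug precaution.
- *That infections are a comparable omission*, because section 3 expects benefit "while not worsening the rates of infectious or other complications". That phrase is rationale and matches no objective. Fatal infections are recorded as deaths and serious ones as SAEs. An uncontrolled count within each arm could not show that rates had not worsened.
- *That a numerical upper bound on the hyperstimulation rate is lost.* Such a bound would need an assumed share of women and pooling of arms that the protocol treats as independent.

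The reply does not explain why one DLT type is treated differently from the other two, or why a named paediatric reaction is left off. The scheduled hormone measurements show exposure to an effect; they do not count clinical signs. No section directs routine recording of non-serious events outside the list.

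**Conclusion.** The point holds as a gap in systematic collection, limited to non-serious ovarian hyperstimulation (in phase II, and in phase I after day 21) and to precocious puberty throughout. As written, the plan cannot estimate rates for either. The uncovered period is 43-50% of doses in responders who complete maintenance, given the dosing-gap assumption above, and all doses in patients enrolled after phase I. The number of women and pre-pubertal children affected cannot be derived from the documents and may be small. The primary response endpoint is untouched. What changes is how far the secondary safety objective and the phase II aim of confirming safety can be answered for effects that the protocol itself names.

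**What to change.** Add two lines to the 11.2 list, for both phases, from dose one until four weeks past the final dose:

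1. Ovarian hyperstimulation, with its grade on the generic scale already printed in 11.2.
2. Signs of precocious puberty in pre-pubertal patients.

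Include both in the 13.3 safety summary by arm, with the number of patients at risk as the denominator (females; pre-pubertal patients). The sponsor must also reconcile the hyperstimulation DLT definition across the synopsis, 7.1-7.3, 11.2 and 13.1; which wording applies is for the sponsor to decide.

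The cost is two more form fields abstracted from the chart, with no added visit.

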11.3 Institutional Event Reporting Table

Individual institutional sites will be responsible for reporting any event meeting local reporting requirements to their institutional IRB and/or other research oversight committees.

Additionally institutional sites will be responsible for reporting events detailed in [sections 11.1](#) and [11.2](#) within the following time frames to the MCC Affiliate Sites Manager

Event Type	Reporting Timeframe	Form in OnCore to Use	Report to
Any event meeting the definition of a SAE within 4 weeks after last dose of pregnyl	Within 24 hours of knowledge	SAE Report Form	Masonic Cancer Center (MCC) Affiliate Sites Manager [contact] Local institutional IRB or other entities per institutional policies and guidelines.
Event counting toward the safety stopping rule as defined in Section 13.4	Within 24 hours of knowledge	Stopping Rule Event Form	
Major Deviations, as defined in Section 11.1 .	Within 5 working days of knowledge	Deviation Report Form	
Minor Deviations, as defined in Section 11.1 .	Per Institutional Policy	n/a (record in Deviations Tab) but it is not necessary to report the event to MCC	For UMN MCC only: minor deviations are reported to the UMN IRB by the study's regulatory specialist per IRB reporting requirements. For Affiliate Sites: minor deviations are not reportable to the Masonic Cancer Center. Report to local institutional IRB or other entities per institutional policies and guidelines.

11.4 Required Reporting: FDA, IRB and Masonic Cancer Center's SAE Coordinator

As the study sponsor, the Masonic Cancer Center has the following expedited reporting responsibilities for local events and events reported in [Section 11.3](#).

Agency	Criteria for reporting	Timeframe	Form to Use	Submission address/ fax numbers
U of MN IRB	Events requiring prompt reporting including, but not limited to unanticipated death of a locally enrolled subject(s); new or increased risk; any adverse event that require a change to the protocol or consent form or any protocol deviation that resulting in harm refer to http://www.research.umn.edu/irb/guidance/ae.html#.VC7xral0-sh	Within 5 business days of event discovery	IRB's Report Form	[contact]
FDA	Unexpected and fatal or life threatening suspected adverse reaction	As soon as possible but no later than 7 Calendar-Days	MCC SAE	Submit to CBER as an amendment to IND
	1) Serious and unexpected suspected adverse reaction or 2) increased occurrence of serious suspected adverse reactions over that listed in the protocol or investigator brochure or 3) findings from other sources (other studies, animal or in vitro testing)	As soon as possible but no later than 15 Calendar-Days		
	All other events per CRF 312.33	At time of IND annual report	Summary format	Submit as part of the IND annual report
Masonic Cancer Center SAE Coordinator	Events that meet the criteria of dose limiting toxicity (DLT) or an early study stopping rule	At time of reporting	Event Form	SAE Coordinator [contact]

In each IND safety report, the sponsor must identify all IND safety reports previously submitted to the FDA concerning a similar suspected adverse reaction and must analyze the significance of the suspected adverse reaction in light of the previous, similar reports.

The SAE Coordinator will provide the Masonic Cancer Center's Data and Safety Monitoring Council (DSMC) with the SAE in an appropriate format depending on the individual SAE (as reported or in a summary format).

12 Study Data Collection and Monitoring

12.1 Data Management

This study will report clinical data using The Online Enterprise Research Management Environment (OnCore™), a web based Oracle® database utilizing study specific electronic case report forms. Key study personnel are trained on the use of OnCore and will comply with protocol specific instructions embedded within the OnCore. Patient demographics, patient specific study treatment calendars, targeted adverse events and other information required for IND annual reporting will be placed in OnCore and other databases maintained by the Cancer Center.

12.2 Case Report Forms

Participant data will be collected using protocol specific electronic case report forms (e-CRF) developed within OnCore based on its library of standardized forms. The e-CRF will be approved by study's Principal Investigator and the Biostatistician prior to release for use. The Study Coordinator or designee will be responsible for registering the patient into OnCore at time of study entry, completing e-CRF based on the patient specific calendar, and updating the patient record until patient death or end of required study participation.

12.3 Data and Safety Monitoring Plan (DSMP)

The study's Data and Safety Monitoring Plan will be in compliance with the University of Minnesota Masonic Cancer Center's Data & Safety Monitoring Plan (DSMP), which can be accessed at <http://z.umn.edu/dmsp>.

For the purposes of data and safety monitoring, this study is classified as high-risk (phase I). Therefore the following requirements will be fulfilled:

- The PI will complete and submit a quarterly Trial Progress Report to the Masonic Cancer Center Data and Safety Monitoring Council (DSMC) with the understanding the Cancer Protocol Review Committee (CPRC) may require more frequent reporting.
- The PI will comply with at least twice yearly monitoring of the project by the Masonic Cancer Center monitoring services.
- The PI will oversee the submission of all reportable adverse events per the definition of reportable in [section 11.1](#) to the Masonic Cancer Center's SAE Coordinator, the University of Minnesota IRB, and the FDA.
- The PI with the CTO has oversight responsibility for trial monitoring at affiliate sites.

In addition, at the time of the continuing review with the University of Minnesota IRB, a copy of the report with any attachments will be submitted to the Cancer Protocol Review Committee (CPRC).

